The two long chain omega-3 (n-3) fatty acids of most importance to human health are eicosapentaenoic acid (EPA; 20:5n-3) and docosahexaenoic acid (DHA; 22:6n-3). These fatty acids have been shown to lower risk of morbidity and mortality from cardiovascular disease [1-3]. They exert their protective effects by beneficially altering some of the recognised cardiovascular risk factors [1,2,4]. These fatty acids also exert benefit in inflammatory conditions [5] and perhaps in some cancers [6]. There is emerging evidence that they are important in development of learning and behaviour in childhood [7], in preventing psychiatric and psychological disorders in adults [8] and in slowing cognitive decline in the elderly [9]. As a result of these beneficial effects on human health, particularly the cardioprotective effects, there have been recommendations that individuals should increase their intake of long chain n-3 fatty acids [1,10-14]. The only naturally rich source of EPA and DHA is seafood, especially oily fish. Thus one strategy to increase intake of these fatty acids is to increase fish consumption, and there are recommendations to do so [13,14]. However, many consumers are resistant to taking this option despite the likely benefit. Also the n-3 fatty acid content is highly variable amongst fish species and even within species depending upon time of year, location at which caught etc. Thus, consumption of oily fish once or twice a week as recommended results in irregular intake of an unknown (to the consumer) amount of EPA plus DHA. In addition, some fish species are contaminated with heavy metals and other pollutants [13] and so their intake should be limited [13,14]. An alternative strategy to increase EPA plus DHA intake is to supplement with "fish oil" capsules. These present a useful strategy because capsules can provide a regular (daily) intake of a known amount of n-3 fatty acids. Furthermore, because of fish oil processing technologies, contaminants are removed, and so capsules represent a safe alternative to fish. There are many "fish oils" available and these present the n-3 fatty acids largely in one of two forms, as components of triglycerides (TAGs) or as ethyl esters (EEs). In addition to these forms of presentation, encapsulated n-3 fatty acids in the form of phospholipids (PLs) and of free fatty acids (FFAs) are also available commercially and have been used experimentally. An important question that is thus far not resolved is whether EPA and DHA are equally well incorporated into human blood, cells and tissues when presented in the form of TAGs, EEs, PLs

and FFAs. The literature is not clear about this, with better availability from TAGs being reported in some studies in rats [15,16], better availability from PLs being reported in humans [17], and similar availability from TAGs and EEs being reported in other studies in rats [18] and in humans [19,20]. Reasons for the differences between studies probably relate to differences in how studies were done and how data are reported and interpreted. The n-3 fatty acids can be interesterified between different positions in the parent TAG molecule and this is done in some supplements to increase n-3 fatty acid bioavailability; specifically it is believed that the fatty acid at the 2-position of the TAG has better bioavailability. Whether EPA and DHA are equally available, or not, when presented in different forms is an important scientific question. We believe that the answer to this question is very important to regulators, advisors and consumers, as well as to those involved in the fish oil industry. Therefore, we propose to conduct research in human volunteers that will address this question. We plan to investigate the appearance of EPA and DHA in the bloodstream over a period of weeks of consumption of those fatty acids in different chemical forms.

8. Objectives

The overall objective will be to follow the appearance of EPA and DHA in blood components when the fatty acids are consumed either as TAGs (two different formulations, one with the n-3 fatty acids interesterified and one without this modification), EEs, or FFAs.

The specific objectives are:

- 1. To follow the appearance over several weeks in plasma lipids and blood cells of EPA and DHA consumed as components of either TAGs or EEs or FFAs.
- 2. To follow the effect of the different omega-3 formulations on blood markers of inflammation (e.g. cytokines, adhesion molecules).

9. The study

General approach to be taken

Long term (several weeks to several months) studies are required to investigate and to compare the incorporation of n-3 fatty acids into transport pools (blood lipids) and functional pools (e.g. cells) which is a true measure of n-3 status. When included in the human diet EPA and DHA are incorporated into plasma lipid fractions, platelets, white cells, red cells and many other cell and tissue types. We have studied the detail of such fatty acid incorporation, particularly for plasma phospholipids and for white blood cells in at least eight studies in human volunteers and also in patients with advanced atherosclerosis and with Crohn's Disease. In these studies fish oil supplements of various types (but almost exclusively in the TAG form) have been used with blood being sampled at various time intervals over the course of several months. We have reported both the time- and dose-dependent nature of the incorporation into plasma phospholipids and white blood cells (e.g. see [21]). Incorporation of EPA and DHA is typically detectable within weeks. However the rate of incorporation and the time to reach a maximum varies according to turnover of the pool investigated. Thus incorporation into white cells is faster than into red cells. We will use the general approach used in our previous studies with human volunteers to investigate the appearance in plasma lipids (phospholipids, TAGs, cholesteryl esters, NEFAs, EEs), in white cells (mononuclear cells) and in red cells of EPA and DHA when supplemented in the TAG or EE or FFA form.

Subjects and supplements

Healthy males and females aged 18 to 45 years with a body mass index between 20 and 32 kg/m^2 (n = 100) will be recruited. Subjects will recruited via posters; email shots in the University of Southampton, Southampton General Hospital, and other organisations with which the researchers have contact; advertisements in local newspapers. Subjects who express an interest will be screened by telephone interview. If they fit the inclusion and exclusion criteria (see below) they will be sent the information sheet. They will be contacted about 7 days later to confirm their interest or not, and if they remain interested an appointment will be made for them to visit the Wellcome Trust Clinical Research Facility, Southampton General Hospital.

Recruited subjects will be randomised to one of five groups (n = 20 per group):

- Placebo
- Omega-3 ethyl esters
- Omega-3 free fatty acids
- Omega-3 triglycerides (standard formulation)
- Omega-3 triglycerides (interesterified formulation).

The n-3 fatty acid preparations to be used are all commercially available as supplements and will be provided in capsules. Approximately 1.5 g EPA plus DHA (approx. 1.1 g EPA and 0.4 g DHA) will be given per day. Subjects, researchers and clinical staff will be blinded to group allocation.

Inclusion criteria

- 1. Aged 18 to 45 years
- 2. Body mass index 20 to 32 kg/m^2
- 3. Not consuming fish oil or other oil supplements
- 4. Not eating more than one oily fish meal per week
- 5. Willing to adhere to the study protocol
- 6. Being able to provide written informed consent

Exclusion criteria

- 1. Aged < 18 or > 45 years
- 2. Body mass index $< 20 \text{ or} > 32 \text{ kg/m}^2$
- 3. Being diabetic (type 1 or type 2)
- 4. Use of prescribed medicine to control inflammation
- 5. Chronic gastrointestinal problems (e.g. IBD, IBS, celiac disease, cancer)
- 6. Allergic to fish
- 7. Participation in another clinical trial
- 8. Use of fish oil or other oil supplements

Subject participation schedule

Subjects who express an interest will be screened by telephone interview. If they fit the inclusion and exclusion criteria they will be sent the information sheet. They will be contacted about 7 days later to confirm their interest or not and if they remain interested an appointment will be made for them to visit the Wellcome Trust Clinical Research Facility, Southampton General Hospital. At the first (and all subsequent) visit, subjects will attend in the fasted state (no food or drink except water after 9 pm the previous evening).

Subjects will visit the Wellcome Trust Clinical Research Facility, Southampton General Hospital on six occasions each between 8 and 10 am. On each occasion they will be in the fasted state. Visits will be at study entry and after approx. one, two, four, eight and twelve weeks of supplementation. On each occasion blood (20 ml) will be taken into heparin; at the visit made at study entry height and weight will be measured. At the end of each visit subjects will be offered toast and a hot drink. Subjects will receive a supply of supplements along with instructions on how to take them at the first study visit.

Sample analysis

Blood will be used to prepare plasma, mononuclear cells and red cells. Plasma will be aliquoted and frozen at minus 80°C. Mononuclear cells will be frozen at minus 80°C. Red cell membranes will be prepared using standard techniques currently in use in the PI's lab and then frozen at minus 80°C. Lipid will be extracted from plasma, mononuclear cells and red cells using chloroform/methanol. Plasma TAGs, PLs, NEFAs and EEs will be isolated by solid phase extraction [21]. The fatty acid composition of plasma TAGs, PLs, NEFAs and EEs and of mononuclear cells and red blood cells

will be determined by gas chromatography. Inflammatory marker concentrations in blood will be measured by flow cytometry.

10. Data handling and record keeping

- All data will be entered onto a spreadsheet (Microsoft Excel) by the researchers involved.
- All data will be entered on a password-protected computer. This data will be accessed only by the PI and the researchers involved.
- All data will only be linked to study codes and thus not identifiable with the source volunteer. However, the caveat to this will be a data set recording the volunteer name and study code without any other volunteer details.
- All data recorded on paper will be kept in a locked filing cabinet in the researchers' office and/or in a dedicated, restricted access, clinical data storage area on Level D of the IDS Building, University of Southampton.
- Data of an identifiable nature (i.e. volunteer names, contact details, addresses) will be destroyed 12 months after the end of the study. All other data will be kept securely for 15 years and then destroyed.
- Data will be obtained, handled and stored in adherence to the principle set out in the Data Protection Act 1998.
- The investigators and the Institute of Human Nutrition will permit monitoring, audits, REC and MHRA review (as applicable) and provide direct access to source data and documents.

11. Statistical Analysis

The statistical analysis will involve:

- comparison of the change in EPA content of plasma phospholipids from study entry to week 12 between the different treatment groups (the primary outcome). This will be performed by one factor ANOVA.
- comparison of the change in EPA content of each of the other plasma lipid pools and of mononuclear cells and red blood cells from study entry to week 12 between the different treatment groups (the primary outcome). This will be performed by one factor ANOVA.
- comparison of the change in DHA content of each of the plasma lipid pools and of mononuclear cells and red blood cells from study entry to week 12 between the different treatment groups (the primary outcome). This will be performed by one factor ANOVA.
- comparison of the change of the EPA and DHA contents of each plasma lipid pool and of mononuclear cells and red blood cells over time following consumption of n-3 fatty acids in each chemical form. This analysis will be performed using two-factor repeated measures ANOVA, the two factors being time and group (i.e. "treatment").
- comparison of the change over time in blood concentrations of inflammatory markers according to treatment group. This analysis will be performed using two-factor repeated measures ANOVA, the two factors being time and group (i.e. "treatment").

All statistical comparisons will be performed at the end of the study using SPSS.

12. Sample size calculation

The study is powered according to the anticipated change in EPA content of plasma phospholipids (this is similar to the anticipated change in EPA in mononuclear cells and in red cells). Based upon previous studies of this sort, a supplement providing 1.1 g EPA/day is expected to increase the EPA content of plasma phospholipids by 100% from approximately 1 to approximately 2% of total fatty acids. It is considered that a 25% lower incremental increase in EPA content is meaningful. Typical standard deviations for the incremental increase in EPA content of plasma phospholipids from our previous studies are approximately 0.25%. Thus, sample size was calculated using mean values of 1 and 0.75 for the two groups, respectively, and standard deviations of 0.25 for each group. A sample size calculator revealed that a sample size of 17 per treatment group will give 90% power of

detecting this effect (i.e. a 25% increase) as statistically significant, by a pairwise comparison and setting P < 0.05, as is usual. In order to allow for a drop-out rate of 20% 20 subjects per group will be recruited (100 subjects in total).

13. Safety assessments

The supplements to be used are commercially available and are safe. The sole invasive procedure to be used is obtaining blood samples; this will be done by trained nursing staff limiting the likelihood of adverse events related to participation in the study. However if any volunteer reports any untoward medical occurrence this will be recorded on an adverse event or serious adverse event form and the PI informed immediately. If the investigator suspects that a serious adverse event is either a) related to the intervention or b) unexpected, the PI will report the event to the main REC and to a representative of the supplier of the supplements. An adverse or serious adverse event may result in the volunteer wishing to withdraw from the study or being unable to continue with the study schedule. In this case or any other instance in which a subject withdraws or is withdrawn from the study a volunteer withdrawal form will be recorded on the form. The subject will not be required to give any reason for withdrawing themselves from the study and will not be asked to do so by the investigator.

14. Stopping/Discontinuation of intervention

Completion of each subject's involvement in the study will be when the last blood sample is taken, which will be approx. 12 weeks after the subject entered the study. If there is any reason for discontinuing the intervention prior to its completion the PI will arrange for the research team to inform all volunteers immediately. The PI will also inform the sponsor and the main REC.

15. Monitoring

The project will be overseen and monitored by the Southampton University Hospitals Trust R&D Office.

Steps taken to ensure quality of research

Standard operating procedures will be developed for all aspects of the study. Staff will be fully trained in all procedures in which they are involved. All activities will conform to local health and safety regulations and staff will be adequately trained in these. Good clinical practice and good laboratory practice will be used throughout the study. Staff involved in blood sampling will be properly trained for this. All study samples will be labelled clearly, uniquely, accurately and durably using distinctive water resistant labels printed via computer. All samples will be tracked. The temperatures of fridges and freezers in which samples are stored will be monitored to ensure proper functioning. All analyses will be conducted to the highest standards. All equipment to be used is modern, in good working order and maintained on service contracts. All pipettes to be used are serviced regularly. All data will be recorded in laboratory notebooks that will be signed off by the PI at regular intervals. Data entry into spreadsheets will be carefully monitored. All data will be stored securely.

16. Ethical considerations

The study will involve the participants consuming supplements over the course of several weeks and providing a series of blood samples. Participants will not be aware of which supplements they are taking at any given visit. Participants will be given an information sheet outlining the nature of the study and they will have the opportunity to discuss any issues they may have with the research staff. Participants will most likely be familiar with having blood sampled. Trained researchers will address any concerns that the participants may have. If they remain concerned they will be reminded that they can opt out of any procedure at any time.

17. This study will be conducted in accordance with approvals from the LREC and the Southampton University Hospitals Trust R&D Office.

18. This study will be conducted in compliance with the Research Governance Framework for Health and Social Care, the Medicine for Human Use (Clinical Trials) Regulation 2004 and ICH GCP.

19. Financial arrangements

This study is funded by Vifor Pharma, a producer of dietary supplements.

20. Indemnity

University of Southampton insurance will apply; since an NHS Trust will act as study sponsor, CNST may also apply. University of Southampton insurance may also apply where the cause of harm was not due to clinical negligence as covered by CNST.

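### The primary week-12 ANOVA, run as written, leaves out drop-outs' earlier samples; a repeated measures model using all visits would be a cheap improvement

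*Protocol*

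**What the plan says.** Section 11 of the protocol sets the primary analysis as "comparison of the change in EPA content of plasma phospholipids from study entry to week 12 between the different treatment groups (the primary outcome") and names the test: "This will be performed by one factor ANOVA". The same label is attached to other comparisons in that section; this point concerns only plasma phospholipid EPA, the outcome on which section 12 bases the sample size.

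On allocation, section 9 says: "Recruited subjects will be randomised to one of five groups (n = 20 per group"). On sampling it says: "Visits will be at study entry and after approx. one, two, four, eight and twelve weeks of supplementation". Four post-entry samples are therefore due before week 12. Section 11 uses the time course in a two-factor repeated measures ANOVA, but lists that as a separate analysis and not as the basis of the primary contrast.

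Section 12 needs 17 per group and then adds: "In order to allow for a drop-out rate of 20% 20 subjects per group will be recruited (100 subjects in total"). Section 13 foresees early departure: "An adverse or serious adverse event may result in the volunteer wishing to withdraw from the study or being unable to continue with the study". It also says that reasons for withdrawal will not be sought. Section 16 adds, for participants with concerns about blood sampling: "If they remain concerned they will be reminded that they can opt out of any procedure at any time".

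**The concern.** A change from entry to week 12 cannot be computed for someone who gives no week-12 sample. Unless a value is supplied by some other means, the one-factor ANOVA runs on completers. Section 12 treats drop-out purely as lost numbers, which fits that reading.

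Two things are at stake. First, efficiency: a subject who leaves after week 4 or week 8 has given samples that say something about the week-12 value, and the only powered comparison does not use them. Second, comparability: the arms are different chemical forms of a supplement. If those who leave one arm tend to be its poor incorporators, that arm's completers flatter it and the difference between forms shrinks. Recruiting more subjects restores precision, but it does not correct that. Because reasons for withdrawal are not collected, the earlier EPA values would be the main evidence on whether leavers differed.

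**Working it through.** **Inputs from the protocol.** Increments 1 and 0.75 (difference 0.25), SD 0.25, 17 per group needed for 90% power, 20 per group recruited, 20% drop-out (section 12); post-entry visits at weeks 1, 2, 4, 8 and 12 (section 9).

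**Assumptions, not in the protocol.** Four drop-outs per arm; last sample at week 2, 4 or 8; SD 0.25 at every visit; between-visit correlation 0.5 to 0.85, either the same for all pairs of visits (compound symmetric) or decaying with visit order (AR(1)). The bias simulations also assume a mean profile of 40%, 60%, 85%, 100% and 100% of the final increment.

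**1. The plan's own figure.** The standardised difference is 0.25/0.25 = 1.0. Section 12 does not state sidedness. One-sided, 17 per group gives 89.8% power (normal approximation) or 88.7% (t-test), so the stated 90% is matched within tolerance. Two-sided, 17 gives 83.0% or 80.7%. That gap is a separate matter. The powers below are for the two-sided t-test, since the planned ANOVA is non-directional.

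**2. Completers at week 12.** 20 × 0.80 = 16 per group, 80 of 100 overall. Power with 16 is 78.1%, against 80.7% with 17. The standard error of a pairwise difference is √(2 × 0.25²/16) = 0.088.

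**3. Drop-out unrelated to uptake.** Let R² be the share of week-12 variance explained by the visits a drop-out did attend. With the covariance treated as known, the variance of an arm's week-12 mean is SD² × [(1 − R²)/16 + R²/20], so

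effective n = 1 / [(1 − R²)/16 + R²/20].

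- Least favourable: AR(1), correlation 0.5, last sample at week 2, three visits before week 12. R² = (0.5³)² = 0.0156. Effective n = 1/(0.9844/16 + 0.0156/20) = 16.05; power about 78%.
- Most favourable: compound symmetric, correlation 0.85, last sample at week 8. R² = 4 × 0.85²/(1 + 3 × 0.85) = 0.814. Effective n = 1/(0.186/16 + 0.814/20) = 19.1; power about 85%, standard error √(2 × 0.25²/19.1) = 0.081.

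**4. Drop-out in the worse arm only, driven by low week-2 values.** If the lowest 20% on the week-2 value leave, the completers' week-12 mean rises by about r × 0.25 × φ(z)/0.80 = 0.0875r. Here r is the week-2 to week-12 correlation, z the 20% point of the normal distribution and φ its density.

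- r = 0.125 gives a bias of 0.011, so the true 0.25 is estimated as about 0.24.
- r = 0.85 gives 0.074, so about 0.18 if selection is exact. Noise in the selection weakens this.

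Simulation with noisy selection gives 0.190 to 0.239 for completers and 0.248 to 0.251 for the all-visit estimate. The largest bias, 0.06, is about 0.7 of the completers' standard error (0.06/0.088). When the covariance is estimated from five arms of 20, the all-visit model still gives about 0.24 to 0.25 against 0.19 to 0.22 for completers, with an equal or slightly smaller standard error.

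**5. Other drop-out mechanisms, also simulated.**

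| Mechanism | Completers-only | All-visit |
|---|---|---|
| Low week-2 value, worse arm only | 0.190 to 0.239 | 0.248 to 0.251 |
| Low week-2 value, both arms alike | 0.248 to 0.256 | essentially unbiased |
| Low week-12 value itself, worse arm only | 0.171 to 0.181 | 0.176 to 0.238 |

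The true difference is 0.25 in every row.

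**The case against.** The strongest reply concerns scope. Analysis sets and missing-data rules are commonly left to a SAP, which may exist, and their absence from a protocol is no fault. A SAP could also impute week-12 values and run the same ANOVA, so section 11 does not itself order deletion. This stands. A reader might infer that the protocol is defective because withdrawal, inability to continue and opting out have no stated handling in the primary outcome; the protocol alone does not support that.

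A reader might also infer that 20% drop-out leaves the trial unable to deliver its primary outcome. It does not. Section 12 allows for drop-out, and the expected shortfall is one subject per group (16 against 17), costing 2.6 points of two-sided power. Most of the distance from 90% to 78% comes from the sidedness question, not from missing samples.

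Nor is bias shown. Subjects and staff are blinded, chronic gastrointestinal problems and fish allergy are exclusions, and no section says that drop-out differs by form. The one-arm, week-2 mechanism is the setting in which an all-visit model does best. With the same mechanism in both arms, the completers' contrast is essentially unbiased.

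What survives is narrower. The named test, run as written, uses none of the drop-outs' post-entry data. An alternative exists that performs about as well or better in every scenario examined and needs no new data.

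**Conclusion.** The point holds as a worthwhile improvement to the choice of primary analysis, not as an error. If drop-out is unrelated to uptake, the gain runs from almost nothing (effective 16.05 per group, 78% power) to about three subjects per group (19.1, 85%); the upper end needs high correlation and late drop-out. If low early uptake drives drop-out in the worse arm only, the all-visit model removes a bias of roughly 0.01 to 0.06 in a difference of 0.25. If drop-out depends on the unobserved week-12 value, it reduces the bias, sometimes barely, and does not remove it.

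The correlations, visit profile and drop-out mechanisms are assumptions; only the increments, SD, group size, visit schedule and drop-out rate come from the protocol. The effective numbers also treat the covariance as known, so they are slightly optimistic.

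**What to change.** In section 11, make the primary analysis of plasma phospholipid EPA a likelihood-based repeated measures model of change from entry at weeks 1, 2, 4, 8 and 12, with group, visit, group-by-visit interaction and an unstructured covariance. Include every randomised subject with an entry sample and at least one later sample. Take the group contrasts at week 12 as the primary result. Keep the week-12 one-factor ANOVA as a sensitivity analysis.

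The cost is a few lines of text and slightly more analysis. The model runs in SPSS, which the protocol already names, and no extra subjects, visits or samples are needed. There are three limits: it assumes that drop-out depends only on observed values, it must estimate a five-visit covariance from about 100 subjects, and it still leaves out anyone with no post-entry sample.

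### The primary five-group ANOVA includes placebo, so a significant result would not show whether the n-3 formulations differ, and it is not the test that section 12 powers

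*Protocol*

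**What the plan says.** - **Design.** Section 9, Subjects and supplements: "Recruited subjects will be randomised to one of five groups (n = 20 per group"). The groups are placebo, ethyl esters, free fatty acids, standard triglycerides and interesterified triglycerides.
- **Question.** The background, just before section 8, says: "Whether EPA and DHA are equally available, or not, when presented in different forms is an important scientific question". The overall objective in section 8 names only the n-3 forms.
- **Primary analysis.** Section 11, first bullet: "comparison of the change in EPA content of plasma phospholipids from study entry to week 12 between the different treatment groups (the primary outcome"). The method follows: "This will be performed by one factor ANOVA". Section 11 names no contrast, no pairwise test and no restriction to the active arms.
- **Power.** Section 12 says that a supplement with 1.1 g EPA per day "is expected to increase the EPA content of plasma phospholipids by 100% from approximately 1 to approximately 2% of total fatty acids". It then states that "sample size was calculated using mean values of 1 and 0.75 for the two groups", with "standard deviations of 0.25 for each group". The result is 17 per group with 90% power for "detecting this effect (i.e. a 25% increase) as statistically significant, by a pairwise comparison and setting P < 0.05, as is usual". Recruitment is 20 per group, 100 in total, so all five groups are counted.

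**The concern.** A one-factor ANOVA tests whether all group means are equal. With placebo in the set, that hypothesis is false as soon as supplementation raises EPA, which section 12 takes as given. The primary P value would then be small whether or not the formulations differ, and it could not be reported as evidence on the between-form question.

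The effect that section 12 powers (1.00 against 0.75) is a contrast between two formulations, and section 11 contains no test of it. The two sections therefore describe different primary tests. Any claim that one form is better or worse would rest on comparisons whose error rate the primary test does not control.

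**Working it through.** **Inputs.** From section 12: rise in an active arm 1.0, SD 0.25, meaningful difference 0.25, dropout 20%. From section 9: five groups of 20. Completers: 20 × 0.8 = 16 per group. The protocol gives no placebo change; I assume 0 and vary the gap d between active and placebo.

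**1. The plan's own figure.** For one pair, difference 0.25, SD 0.25 and 17 per group, the t-test has 88.6% power one-sided and 80.7% two-sided at 0.05. The stated 90% is approached only by a one-sided test. That is a separate matter, but it confirms that the calculation concerns a single unadjusted pair and not a five-group F-test.

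**2. Five-group F-test with four identical forms.** Noncentrality is λ = n Σ(μᵢ − μ̄)² / σ². For means (0, d, d, d, d), the sum of squares is 0.64d² + 4 × 0.04d² = 0.8d². At n = 16 and d = 1.0, λ = 16 × 0.8 / 0.0625 = 204.8.

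| Gap d | λ, n = 16 | P(reject), n = 16 | P(reject), n = 20 |
|---|---|---|---|
| 1.0 | 204.8 | 1.000 | 1.000 |
| 0.5 | 51.2 | >99.99% | >99.99% |
| 0.25 | 12.8 | 80% | 90% |

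With d = 1.0 and the SD doubled to 0.5, λ is again 51.2 and rejection still exceeds 99.99%.

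**3. Pairwise tests behind that F-test.** There are 4 × 3 / 2 = 6 active pairs. At an unadjusted two-sided 0.05 with the pooled variance (75 df), the critical t is 1.992, which is 1.992 × √2 = 2.817 on the studentized-range scale. The probability that the range of four equal means exceeds this is 0.20. In 100,000 simulated trials per sample size (16, 17 and 20 per group), the rate was 19.9–20.4%, the same with and without the five-group F-test as a gate. A four-arm F-test as gate brought it to 4.9%; Tukey over the four active arms gave 4.9–5.0%.

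**4. Power of the tests that do address the question.** Tukey over four arms at n = 16 (60 df): critical t = 3.737 / √2 = 2.643; noncentrality = 0.25 / (0.25 × √(2/16)) = 2.828. Power for a 0.25 difference is 58%. At 17 per group it is 61%, and at 20 it is 70%.

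The four-arm F-test (3 df) depends on where the other means lie. At n = 16:
- means (0.75, 1, 1, 1): sum of squares 0.046875, λ = 12.0, power 81%;
- means (0.75, 0.875, 0.875, 1): sum of squares 0.03125, λ = 8.0, power 62%.

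**The case against.** The strongest reply is that section 11 need not settle everything. It states no pairwise procedure, adjusted or not, and a statistical analysis plan that is not shown may specify one. A reader might infer that the protocol prescribes six unadjusted tests after the ANOVA. It does not: the only pairwise wording is the sample-size premise in section 12. The 20% is therefore conditional, and a Tukey or Bonferroni step would remove it. That part of the reply stands. It does not rescue the primary test, because the five-group ANOVA is fixed in this protocol and a later post hoc step would not make its P value informative about formulations.

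It could also be said that treatment groups means the active arms only. The text does not exclude placebo, and section 12 uses the same term while arriving at 100 subjects in five groups, so the five-group reading is the natural one. If four arms were intended, the wording still needs to say so.

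Two further inferences are tempting but unsupported:
- That placebo changes vary less, so the pooled variance understates the error of formulation contrasts. The protocol gives no placebo SD.
- That the repeated-measures analysis of EPA and DHA fails in the same way. That bullet speaks of n-3 consumption in each chemical form and can be read as covering the active arms only.

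**Conclusion.** The concern holds for the primary test. On the protocol's expected rise and SD, the five-group F-test is practically certain to reject when all four forms are identical, so it does not answer the stated question. It also differs from the comparison that section 12 powers.

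The result rests on placebo being in the ANOVA and on an assumed placebo change near 0. It is robust to a gap as small as 0.5; at a gap of 0.25, a quarter of the expected rise, rejection is still 80% at 16 per group. The multiplicity figure of about 20% applies only if the six active pairs are tested at an unadjusted 0.05.

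**What to change.** **Section 11.** Define the primary comparison as the week-12 change in plasma phospholipid EPA among the four n-3 arms only (one-factor ANOVA, 3 df). Follow it with the six pairwise differences under a family-wise adjustment such as Tukey. Keep placebo as a separate reference comparison.

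**Section 12.** Restate power for the test actually used. For a 0.25 difference with SD 0.25, Tukey-adjusted pairwise power is about 58%, 61% and 70% at 16, 17 and 20 per group. If an F-test power is quoted, give the assumed means with it; 81% on its own would hide the 62% that applies when the other two forms lie midway.

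**Cost.** Wording in two sections, with no extra subjects or data. The downside is that the stated power for an adjusted pairwise claim falls well below 90%. Keeping 90% for such a claim would need about 31 completers per active arm, so the sponsor should either accept the lower figure openly or revisit the sample size.
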